5.9.2 Analysis of Concentration-Response Relationship

The concentration-response (C-R) relationship will be analyzed by comparing the time course of mean (\pm SD) percent (%) change from baseline in IGA, EASI or Pruritus NRS (linear scale) with that of the mean (\pm SD) functional dupilumab concentrations in serum (linear scale). Observed data will be used for these analyses.

The concentration-response relationship analyses will be implemented for patients in the PK population with at least one non-missing IGA, EASI, or pruritus NRS value, as applicable for the each concentration-response assessment. Hence, there may be modest differences from the primary efficacy analysis due to the differences in the analysis populations. Patients will be analyzed according to the treatment actually received.

No formal statistical testing will be performed.

6 DATA CONVENTIONS

The following analysis conventions will be used in the statistical analysis.

6.1 Definition of Baseline for Efficacy/Safety Variables

Unless otherwise specified, the baseline assessment for all measurements will be the latest available valid measurement taken prior to the administration of study drug. If any randomized patients are not treated, the baseline will be the last value on or prior to the randomization. The baseline of NRS is defined in [Section 4.4.2](#). The following rules specify the determination by both date/time information:

1. For the AE, lab (including biomarker), PK and ADA data, both date and time of the measurement will be used to determine baseline by comparing with the first injection date and time.
2. For other data except AE, lab (including biomarker), PK or ADA, only date of the measurement will be used to determine baseline by comparing with the first injection date (equal or less than the first injection date).

For the rescreened patients, all data from the same patient will be used to derive baseline regardless if the data is from the screen- failure patient ID or enrolled patient ID.

6.2 General Data Handling Conventions

For the laboratory safety variables and biomarker data, if the data below the lower limit of quantification (LLOQ) / limit of linearity, half of the lower limit value (i.e., LLOQ/2) will be used for quantitative analyses. For data above the upper limit of quantification (ULOQ) / limit of linearity, the upper limit value (i.e., ULOQ) will be used for quantitative analyses.

6.3 Data Handling Convention Missing Data

Missing data will not be imputed in listings. This section includes the methods for missing data imputation for some summary analyses, if necessary.

Adverse event

If the intensity of a TEAE is missing, it will be classified as “severe” in the frequency tables by intensity of TEAE. If the assessment of relationship of a TEAE to the investigational product is missing, it will be classified as “related” in the frequency tables by relation to the investigational product.

Adverse event start date

AE start date will be used for AE classification and analysis of AESIs. If AE start date is not complete, then the character variable will keep the original incomplete date, the numerical date variable will be imputed and an imputation flag will indicate which date component is missing.

If AE start day is missing, and AE start month and year are not missing: If AE start year is the same as first dose year and the AE start month is the same as the first dose month, then impute AE

start day using the day of first dose. If this leads to a date after the AE end date, use AE end date instead. Otherwise impute the AE start day using the first day of the month. If this leads to a date before informed consent, the informed consent date will be used. Imputation flag is 'D'.

If AE start month is missing, and AE start year is not missing: If AE start year is less than the first dose year, use the informed consent day and month. If AE start year is equal to the first dose year, use the first dose day and month. If this leads to a date after the AE end date, use AE end date instead. If AE start year is after the first dose year, use 01 January. Imputation flag is 'M'.

If AE start year is missing: Impute AE start date using the day of first dose. If this leads to a date after the AE end date, use AE end date instead. Imputation flag is 'Y'.

Adverse event end date

The general recommendation is not to impute AE end date. However, since AE end date will be used for AE starting date imputation, In order to carry through the logic for programming, the following intermediate step will be used. Afterwards, only the original character/numeric date recorded in CRF will be kept in the final analysis dataset.

If AE end day is missing, and AE end month and year are not missing: Impute AE end date using the last day of the month. If this leads to a date after end of study follow up date, use the last study visit date instead.

If AE end month is missing, and AE end year is not missing: Impute AE end date using 31 December as the day and month. If this leads to a date after end of study follow up date, use the last study visit date instead.

If AE end year is missing: Impute AE end date using the end of follow up date.

Medication start and end date missing

To determine whether a medication is pre-treatment medication or concomitant medication or both, the missing medication start date is estimated as early as possible, and the missing medication end date is estimated as late as possible. If the medication start date is missing, the onset day will not be calculated in medication listings.

Prior medication start date

If start day is missing, and start month and year are not missing: Impute the start day using the first day of the month. Imputation flag is 'D';

If start month is missing, and start year is not missing: Impute the day and month using 01 January. Imputation flag is 'M'.

If start year is missing: Impute start date using 2 years before informed consent date. Imputation flag is 'Y'.

A special note: for start date with year missing, the general principle is not to impute. However in order to simplify the programming flow, the imputation is proposed to align with the protocol which specifies to collect up to 2 years prior medication. Since the start date of prior medication will not be used in any analysis, the rule will not impact the analysis result.

Prior medication end date

If end day is missing, and end month and year are not missing: Impute end date using the last day of the month. If this leads to a date on or after first dose intake date, use first dose intake date -1 instead. Imputation flag is 'D'.

If end month is missing, and end year is not missing: Impute end date using 31 December as the day and month. If this leads to a date on or after first dose intake date, use first dose intake date -1 instead. Imputation flag is 'M'

If end year is missing: Impute end date using the first dose intake date -1. Imputation flag is 'Y'.

Concomitant medication start date

The imputation rule for concomitant medication start date is the same as AE start date.

Concomitant medication end date

If end day is missing, and end month and year are not missing: Impute end date using the last day of the month. If this leads to a date after end of study follow up date, use the last visit study date instead. Imputation flag is 'D'.

If end month is missing, and end year is not missing: Impute end date using 31 December as the day and month. If this leads to a date after end of study follow up date, use the last study visit date instead. Imputation flag is 'M'.

If end year is missing: Impute date using the end of last study visit date. Imputation flag is 'Y'.

Medication coding

Medications whose ATC level 4 cannot be coded will be summarized by setting ATC4=ATC2 in the table programs. However, these uncoded ATC level 4 records still need to be confirmed with study DM and study MD.

PCSA

Patients who had post-baseline PCSA but missing baseline value will be regarded as having treatment emergent PCSA.

6.4 Analysis Visit Window

Data analyzed by-visit-analysis (including efficacy, laboratory data, visit sign, ECG, ADA) will be summarized by the study scheduled visits described [Appendix 10.2](#), "Schedule of Event". The analysis visit windows will be exhaustive so that all available values obtained from unscheduled visits, early termination visit (ETV) and end of treatment (EOT)/end of study (EOS) have the potential to be summarized. No analysis visit windows will be applied for the study scheduled visits.

The following analysis visit windows will be used to map the unscheduled visits, ETV and EOT/EOS visits, based on the study day:

Time window for efficacy variables

Visit No.	Visit	Targeted Study Days*	Analysis Window in Study Days		
			IGA, EASI, BSA, POEM, DLQI	EQ-5D	Sick-Leave/Missed School Days
1	Screening	<1	<1		
2	Baseline	1	1	≤1	≤1
3	Week 2	15	[2,22]		
4	Week 4	29	[23, 43]		[2, 43]
5	Week 8	57	[44, 71]	[2, 85]	[44, 71]
6	Week 12	85	[72, 99]		[72, 99]
7	Week 16 (End of Treatment)	113	[100, 127]	[86, 155]	[100, 127]
8	Week 20	141	[128, 155]		[128, 155]
9	Week 24	169	[156, 183]		[156, 183]
10	Week 28 (End of Study)	197	≥184	≥156	≥184

*Study days are calculated from 1st day of dupilumab injection (1st day of randomization if the patient is not treated)

Time window for safety variables

Visit No.	Visit	Targeted Study Days*	Analysis Window in Study Days					
			Vital Signs	Weight	ECG	Hematology and Chemistry	Urinalysis	Serum Pregnancy Test
1	Screening	<1	<1	<1	<1	<1	<1	<1
2	Baseline	1	1	1		1	1	≤1
3	Week 2	15	[2,22]					
4	Week 4	29	[23, 43]					[2, 43]
5	Week 8	57	[44, 71]			[2, 85]		[44, 71]
6	Week 12	85	[72, 99]					≥72

7	Week 16 (End of Treatment)	113	[100, 127]	[86, 155]	[86, 155]	[86, 155]	[2, 155]	[2, 155]	
8	Week 20	141	[128, 155]						
9	Week 24	169	[156, 183]						
10	Week 28 (End of Study)	197	≥ 184	≥ 156					

*Study days are calculated from 1st day of dupilumab injection (1st day of randomization if the patient is not treated)

Time window for other variables

Visit No.	Visit	Targeted Study Days*	Analysis Window in Study Days	
				PK/Drug Concentration, ADA
1	Screening	<1	<1	
2	Baseline	1	1	≤ 1
3	Week 2	15		
4	Week 4	29		
5	Week 8	57		
6	Week 12	85		[2, 99]
7	Week 16 (End of Treatment)	113	[2, 155]	[2, 155]
8	Week 20	141		
9	Week 24	169		
10	Week 28 (End of Study)	197	≥ 156	≥ 156

*Study days are calculated from 1st day of dupilumab injection (1st day of randomization if the patient is not treated)

In general, the following order will be used to select the record for analysis at given visit:

1. Scheduled visit
2. Early termination (ET) or end of study (EOS), whichever comes first if scheduled visit not available
3. Unscheduled visit if both scheduled visit and ETV/EOT/EOS are not available

For the multiple measurements of the same test in the same window, the following rules will be used to pick up the analysis value:

- If multiple valid values of a variable within an analysis visit window, the closest from the target study day will be selected.
- If the difference is a tie, the value after the targeted study day will be used.
- If multiple available values of a variable exist within a same day, then the first value of the day will be selected.

Both scheduled and unscheduled measurements will be considered for determining abnormal/PCSA values from laboratory, vital sign or ECG as well as the baseline values.

For the ePRO data collected daily, the analysis visit windows will be implemented following the procedures below:

Step 1: Derive the study day,

- If diary date \geq 1st injection date, then diary study day=diary date – 1st injection date +1;
- Otherwise diary study day=diary date – 1st injection date

Randomization date will be used instead of 1st injection date for patients randomized but not treated.

Step 2: Windows are defined as -6 to 1 = BL, 2 to 8 = week 1, 9 to 15 = week 2, etc, with 7 days interval between visit windows.

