1.3 Modifications from the Statistical Section in the Final Protocol

Modifications from the Amended protocol 1 (final protocol)

1. concomitant medication/procedure

Any concomitant treatment is considered from the first dose of study drug in the SAP instead of the time of informed consent in the protocol.

2. Potentially clinically significant abnormality (PCSA)

PCSA is applied to clinical laboratory evaluations and vital signs in SAP, while PCSA was applied to ECG as well in the protocol.

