4.5.3 Vital Sign Variables

The following vital signs parameters will be collected:

- Weight (kg) and height (cm)
- Respiratory rate (breaths/min)
- Heart rate (beats/min)
- Systolic and diastolic blood pressures (mmHg)
- Body temperature (°C)

Weight is determined at screening and baseline (Day 1), and Week 16 (EOT), Week 28 (EOS), ET and unscheduled visits. Height is only measure at screening. Other vital signs are collected pre-dose at every scheduled and unscheduled clinic visit.

4.5.4 12-Lead Electrocardiography (ECG) Variable

The ECG interpretation variable are dichotomized to normal and abnormal. Electrocardiograms will be performed before blood is drawn during visits requiring blood draws. A standard 12-lead ECG will be performed at screening, Week 16 (EOT), and Week 28 (EOS) or ET visits.

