5.8.5 Analysis of 12-Lead ECG

Number and percentage of patients with abnormal ECG interpretation will be summarized at baseline, end of treatment period and end of study by treatment group.

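### ECG and weight have no analysis window for Days 2 to 85, so an early-termination ECG from that span has no place in the SAP's only ECG table

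*SAP*

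**What the plan says.** SAP 6.4 describes how post-baseline records are assigned to visits. ECG is named among the data handled this way: "Data analyzed by-visit-analysis (including efficacy, laboratory data, visit sign, ECG, ADA) will be summarized by the study scheduled visits". Records from scheduled visits keep their visit label. Windows are needed only for the rest: "The following analysis visit windows will be used to map the unscheduled visits, ETV and EOT/EOS visits, based on the study day". The stated aim is full coverage: "The analysis visit windows will be exhaustive so that all available values obtained from unscheduled visits, early termination visit (ETV") and EOT/EOS can be used.

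In the table for safety variables, the Week 16 row, read from weight through ECG and hematology/chemistry to urinalysis and serum pregnancy, gives "86, 155] [86, 155] [86, 155] [2, 155] [2, 155". The Week 8 row has a single [2, 85] entry, which belongs to hematology/chemistry.

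On collection, SAP 4.5.4 states: "A standard 12-lead ECG will be performed at screening, Week 16 (EOT), and Week 28 (EOS) or ET visits". SAP 4.5.3 states: "Weight is determined at screening and baseline (Day 1), and Week 16 (EOT), Week 28 (EOS), ET and unscheduled visits".

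On reporting, SAP 5.8.5 plans one ECG output, in which the number and percentage of patients with "abnormal ECG interpretation will be summarized at baseline, end of treatment period and end of study by treatment group". SAP 1.3 records a change from the protocol: "PCSA is applied to clinical laboratory evaluations and vital signs in SAP, while PCSA was applied to ECG as well in the protocol".

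**The concern.** The windows exist so that values taken off schedule, early-termination values in particular, can be summarized. For ECG and weight they miss most of the treatment period. A patient who terminates before Day 86 has an ECG and a weight taken at that visit, and neither can be placed at an analysis visit.

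This matters more for ECG than for weight. With the PCSA analysis of ECG gone, and no treatment-emergent summary or listing of ECG findings described in 5.8.5, the by-visit table is the only place where the SAP reports ECG results as such. If an early leaver does not come back, the termination ECG is the only planned post-dose ECG for that patient. Whether it is tabulated would be left to a programmer's decision that the SAP does not settle.

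**Working it through.** The plan gives no figure to reproduce here. The check is to compare each column's windows with the study days they should cover.

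**Inputs.** The windows come from the two tables in SAP 6.4. Visit schedules come from SAP 4.4.2, 4.5.2 to 4.5.4 and 10.2. The Week 28 row of the safety table is damaged in the available text; I assume its entry of Day 156 onward applies from the weight column rightward. This does not affect Days 2 to 85.

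| Variable | Scheduled post-baseline visits | Windows | Days 2 to 85 uncovered |
|---|---|---|---|
| Hematology/chemistry | Weeks 8, 16, 28 | [2, 85], [86, 155], ≥156 | 0 |
| EQ-5D (efficacy table) | Weeks 8, 16, 28 | [2, 85], [86, 155], ≥156 | 0 |
| Urinalysis | Weeks 16, 28 | [2, 155], ≥156 | 0 |
| ECG | Weeks 16, 28 | [86, 155], ≥156 | 84 |
| Weight | Weeks 16, 28 | [86, 155], ≥156 | 84 |

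Vital signs, with contiguous windows from [2, 22] onward, also have no uncovered day.

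**Size of the gap.** Days 2 to 85 are 85 − 2 + 1 = 84 days. Days 2 to 113 (the Week 16 target) are 113 − 2 + 1 = 112 days. The gap is 84/112 = 75% of that span.

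**Which entry is out of line.** The midpoint of Week 8 (Day 57) and Week 16 (Day 113) is (57 + 113)/2 = 85. The midpoint of Week 16 and Week 28 (Day 197) is (113 + 197)/2 = 155. A window of [86, 155] therefore fits a test that also has a Week 8 visit. Urinalysis has the same scheduled post-baseline visits as ECG and weight, and its window opens at Day 2.

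**Does the damaged table explain it?** No. Three columns carry [86, 155] at Week 16 and only one [2, 85] entry precedes them. However the cells are realigned, two columns are left without cover for Days 2 to 85. Of the three tests, only hematology/chemistry has a Week 8 visit.

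**Which records fall in the gap.** Protocol 10.1.5 lists ECG and weight at the early termination visit. Protocol 10.1.6 lists weight, but not ECG, at unscheduled visits. The early termination visit is therefore the planned source of ECGs in the gap; weights can come from either.

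**With the change.** If the Week 16 window for ECG and weight were [2, 155], uncovered days would fall from 84 to 0.

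**Scale, by assumption only.** The documents give no dropout rate. If 5% to 15% of 160 patients terminated before Day 86, that would be 160 × 0.05 = 8 to 160 × 0.15 = 24 patients. This is an upper bound on patients missing from the table, because those who return at Week 16 supply a scheduled ECG. As an illustration, if 4 of 80 in an arm left early and did not return, the Week 16 denominator would be 80 − 4 = 76.

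**The case against.** The best counter-argument is that 6.4 contains text pointing the other way. After the tables, the record-selection order puts an early-termination or end-of-study record second when the scheduled one is missing, which could be read as letting a termination ECG stand in for Week 16. The same section says that unscheduled as well as scheduled ECGs are considered when abnormal values are determined. SAP 5.8.5 speaks of the end of the treatment period, and SAP 3.3 ends the on-treatment period at early termination if that comes before 14 days after the last dose. A reader could combine these and place the termination ECG at end of treatment.

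Part of this stands: exclusion is not certain. But none of these texts assigns a Day 2 to 85 ECG to a visit. The selection order chooses among records at a given visit, so a record must first have reached that visit. The sentence on abnormal values names no time point, while 5.8.5 reports only by time point. The 6.4 table labels its end-of-treatment row as Week 16. The result is an unresolved conflict.

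The objections on impact stand in full. Patients who stop study drug are asked to attend all remaining visits (Protocol 8.1.4.2 and 10.3.4), and those withdrawn before Week 16 are asked back at Week 16 (Protocol 10.1.5). ECG abnormalities that are symptomatic, need treatment or consultation, lead to a change in study drug, or are serious are recorded as adverse events (SAP 4.5.1) and reach the adverse event tables. Weight PCSA uses every evaluation from first injection to end of study (SAP 5.8 and 10.3).

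A reader might infer that the gap makes the ECG results look safer than they are. The documents do not support that. The same windows apply to both arms, and neither dropout nor ECG abnormality rates are given by arm, so the direction of any bias cannot be stated.

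**Conclusion.** The point holds as a defect in the window table. SAP 6.4 claims exhaustive windows and leaves 84 days uncovered for ECG and weight. Taken literally, it drops an early-termination ECG before Day 86 from the only ECG summary described, and it conflicts with its own sentence on unscheduled ECGs.

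The consequence is modest. It concerns patients who terminate before Day 86 and do not return at Week 16, a number the documents do not give; the 8 to 24 above is an assumed ceiling and should not be read as a count of lost ECGs. What is at risk is mainly a normal/abnormal reading without adverse-event consequences, in a descriptive table. For weight, only the by-visit change from baseline is affected. No efficacy result is touched. The conclusion rests on reading the three [86, 155] entries as weight, ECG and hematology/chemistry, which follows the column order and the visit schedule.

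**What to change.** In the SAP 6.4 table for safety variables, change the Week 16 (End of Treatment) window for ECG and for weight from [86, 155] to [2, 155], as already set for urinalysis. This also removes the conflict with the sentence on unscheduled ECGs, since each post-baseline ECG would then have a visit at which it can be counted.

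The cost is two table cells, with no new data or procedures. The downside is small: a value taken early in treatment would be summarized under the end-of-treatment label when no scheduled Week 16 value exists, as the SAP already accepts for urinalysis. If the sponsor prefers to keep [86, 155], an explicit rule placing ECG and weight values from Days 2 to 85 would serve the same purpose.

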3.4 Pharmacokinetic (PK) Population

The PK population consists of all patients in the safety population with at least one evaluable functional dupilumab concentration result following the first dose of study drug up to Week 16. Functional dupilumab concentration will also be reported in those patients who completed the study through week 28. Patients will be analyzed according to the treatment actually received.

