4.6 Pharmacokinetic (PK) Variables

Pharmacokinetic variables include trough concentration (C_{trough}) over time until week 16. Samples for measurement of functional dupilumab concentration in serum will be collected before the injection of the IMP at baseline (Day 1), Week 12, Week 16 (EOT), Week 28 (EOS), ET and unscheduled visits.

A series of horizontal black bars of varying lengths, likely representing a redacted list of names or information.

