5.9 Analysis of Pharmacokinetic Data

5.9.1 Descriptive Analysis of Dupilumab Concentrations in Serum

Serum concentrations of dupilumab will be summarized in the PK population using arithmetic and geometric means, SD, standard error of the mean (SEM), coefficient of variation (CV, %), median, minimum, first quartile, third quartile and maximum per sampling time by treatment group. If date and/or time of the drug injection and/or sampling is missing then the concentration will not be taken into account. Percentages are rounded to 3 significant figures; therefore, slight differences between subgroups and overall percentages may occur.

Concentrations of functional dupilumab below the lower limit of quantification (LLOQ) are set to zero. Line plots of mean (SD) and median functional dupilumab concentrations will be presented over nominal time (weeks; linear and log scales). Individual line plots of functional dupilumab concentration (spaghetti plots) will be presented over actual time (weeks) on linear and log scales. Individual scatter plots will be presented over nominal time (weeks). When the scale is linear, concentrations below the LLOQ are set to zero. In the log-scaled figures, concentrations below the LLOQ are imputed as LLOQ/2.

[figure not shown]
Dupilumab trough concentration on week 16 will be summarized based on baseline body weight categories (<70 kg, \geq 70-<100 kg, \geq 100 kg).

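### The SAP's PK windows for Week 12 and Week 16 overlap on Days 2 to 99, and its trough summaries set no condition on time since the last dose

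*SAP*

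**What the plan says.** SAP 6.4 treats two kinds of record differently. Scheduled visits keep their nominal label: "No analysis visit windows will be applied for the study scheduled visits". All other records are placed by study day: "The following analysis visit windows will be used to map the unscheduled visits, ETV and EOT/EOS visits, based on the study day".

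In the table for other variables, the column for drug concentration and ADA gives baseline ≤1, Week 12 [2, 99], Week 16 [2, 155] and Week 28 ≥156.

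Within a visit the order of preference is a scheduled record, then "Early termination (ET) or end of study (EOS), whichever comes first if scheduled visit not available", then an unscheduled record. For competing values the rule is: "If multiple valid values of a variable within an analysis visit window, the closest from the target study day will be selected".

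Under SAP 4.6, PK samples are "collected before the injection of the IMP at baseline (Day 1), Week 12, Week 16 (EOT), Week 28 (EOS), ET and unscheduled visits". The PK population in SAP 3.4 needs "at least one evaluable functional dupilumab concentration result following the first dose of study drug up to Week 16", and evaluable is not defined by time since dosing. The only exclusion in SAP 5.9.1 is: "If date and/or time of the drug injection and/or sampling is missing then the concentration will not be taken into account". The same section plans a table by body weight: "Dupilumab trough concentration on week 16 will be summarized based on baseline body weight categories".

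**The concern.** Two visits at which PK is sampled should not claim the same study days. Elsewhere in SAP 6.4, the efficacy columns that contain both Week 12 and Week 16 are disjoint: [72, 99] then [100, 127]. Chemistry, which has Week 8 and Week 16, runs [2, 85] then [86, 155].

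Systemic exposure is a stated objective, and trough concentration up to Week 16 is the PK variable named in SAP 4.6. An early-termination sample drawn a few days after an injection is not a trough, and one drawn in the first weeks is not a Week 12 or Week 16 value. If such samples enter these summaries, the tables mix different quantities, and one sample could appear under two visits. The outputs exposed are the concentration summaries per sampling time, the Week 16 table by weight, and the mean concentration curves in the concentration-response analysis of SAP 5.9.2.

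**Working it through.** **1. Reproduce the windows the SAP uses elsewhere.** The SAP states no formula. A midpoint rule, inferred here, fits: a window ends at the integer part of (target + next target)/2, the next begins a day later, and the first post-baseline window begins on Day 2.

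- IGA/EASI column, targets 15, 29, 57, 85, 113, 141, 169, 197: upper bounds 22, 43, 71, 99, 127, 155, 183. All match the printed windows.
- EQ-5D, targets 57, 113, 197: (57 + 113)/2 = 85 and (113 + 197)/2 = 155. This gives [2, 85], [86, 155], ≥156, which matches.
- The sick-leave column also matches.

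**2. Apply it to PK**, targets 85, 113, 197: (85 + 113)/2 = 99 and (113 + 197)/2 = 155.

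| Visit | Midpoint rule | Printed |
|---|---|---|
| Week 12 | [2, 99] | [2, 99] |
| Week 16 | [100, 155] | [2, 155] |
| Week 28 | ≥156 | ≥156 |

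Only the Week 16 lower bound differs. The rule gives [2, 155] if Week 12 is not a time point.

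**3. Size of the overlap.** Days 2 to 99 are 99 − 2 + 1 = 98 days. The Week 16 window has 155 − 2 + 1 = 154 days. The share is 98/154 = 64%, and 56 days belong to Week 16 alone.

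**4. Follow one sample.** Suppose a patient terminates on Day 20 and does not return.

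- Day 20 is in both windows, 85 − 20 = 65 days from the Week 12 target and 113 − 20 = 93 days from the Week 16 target.
- After a Day 15 dose it is 5 days post-dose. If the Day 15 dose was missed, it is 19 days after Day 1.
- The closest-to-target rule chooses among several values in one window. It does not choose between two windows for one value.
- The missing-date exclusion does not catch a fully dated sample.

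**5. Would correcting the window be enough?** No. Day 20 would leave Week 16 but stay in Week 12 [2, 99]. A condition on time since dose is also needed.

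**6. What condition is compatible with the protocol?** The Week 14 dose is on Day 99 ± 3 (96 to 102) and the Week 16 visit on Day 113 ± 3 (110 to 116). The shortest compliant interval is 110 − 102 = 8 days and the longest is 116 − 96 = 20 days. The 14 ± 3 days in protocol 8.1.3 governs spacing between doses. No dose is given at Week 16, so using 11 to 17 days as a filter there would discard compliant samples.

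**7. Illustrative size.** The documents give no dropout rate, weight distribution or expected concentrations, so these are assumptions. If one of n values equals a fraction x of the true trough and the rest equal it, the arithmetic mean shifts by (x − 1)/n.

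| n in the category | x = 0 | x = 1.5 |
|---|---|---|
| 5 | −20% | +10% |
| 20 | −5% | +2.5% |
| 80 (whole arm) | −1.25% | +0.6% |

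If 0 to 8 of the 80 dupilumab patients (0% to 10%) left before Week 16 and gave no scheduled Week 16 sample, up to 8 values could be affected.

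**The case against.** Several stronger readings are tempting, and the documents do not support them.

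- **That an early-termination sample is always reported as a Week 16 trough.** A scheduled record takes precedence. Protocol 10.1.5 asks patients withdrawn before Week 16 to attend both a termination visit and the Week 16 visit. The problem arises only when the scheduled sample is absent. Even then the SAP does not say whether the value goes to Week 12, Week 16 or both, so double counting is possible but not prescribed.
- **That scheduled Week 12 samples spill into Week 16.** They do not, because scheduled visits are not windowed.
- **That the windows bring in patients who are off IMP.** A patient who stopped early but attends Week 16 gives a scheduled sample, which enters whatever the windows say. With a last dose on Day 15 it is drawn 113 − 15 = 98 days later. That equals the gap from the last planned dose to Week 28 (197 − 99 = 98), by which the protocol expects most levels to be below quantification; SAP 5.9.1 sets such values to zero. Reporting it as observed exposure per sampling time is defensible. Calling it a trough on q2w dosing is not, but that comes from the missing dosing condition and not from the overlap.
- **That ADA results are distorted.** SAP 4.5.6 plans ADA analysis at baseline, Week 16, Week 28 and early termination, not Week 12, so [2, 155] can be right for ADA. Response categories are set per patient across all post-dose samples, so the window does not change them.

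It is also fair to say that the stakes are low, that the word evaluable leaves some room for PK judgement, and that medians and quartiles are reported beside the means. These arguments limit the point. They do not remove the printed overlap or supply the missing rule.

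**Conclusion.** The point holds in a limited form. As printed, the Week 12 and Week 16 windows share Days 2 to 99. When no scheduled sample exists at the visit, one early-termination or unscheduled concentration can be summarised under either visit or both. Separately, nothing in SAP 5.9.1 confines the trough summaries to samples taken at a trough.

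The effect is confined to descriptive PK outputs under an objective classed as other. The primary endpoint, the secondary hierarchy and ADA incidence are untouched. For the arm as a whole, one stray value matters little. In a small weight category it could move the mean noticeably, but the size depends on assumed counts and concentrations.

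The conclusion rests on the column as printed. It reads coherently, but a neighbouring column in the same table has no legible header and also shows [2, 155]. The cell should therefore be confirmed in the source PDF.

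**What to change.** 1. In SAP 6.4, split PK from ADA. For PK, set Week 16 to [100, 155], so that it abuts Week 12 [2, 99]. For ADA, keep windows consistent with the time points in SAP 4.5.6. Moving the shared column to [100, 155] would instead send early-termination ADA samples to Week 12, where no ADA analysis is planned.
2. In SAP 5.9.1, limit the trough summaries, including the Week 16 table by weight, to samples whose time since the preceding IMP dose is compatible with the protocol's dose and visit windows: about 8 to 20 days for Week 16, not 14 ± 3.
3. List early-termination, unscheduled and off-IMP concentrations separately. The time condition alone would not suffice: a termination sample on Day 29 after a Day 15 dose is 29 − 15 = 14 days post-dose, but it is not a Week 12 trough.

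The cost is SAP wording, one extra window column and one programming condition. The downside is a few fewer values in the trough tables; those values remain visible in the listing.
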